- 5) The source documents and relevant CRF pages for this visit will be completed.

V06 (12 months +14 days after VAC2): Collection of Safety Information and Blood Sample - for Adult Subjects in Immunogenicity Persistence and Booster Phase Cohort 2

- 1) DC SAE will be checked by the Investigator/staff, different from the person performing vaccination.
- 2) A blood sample will be collected (6 mL).

- 3) Collect reportable categories 2 and 3 concomitant medications in the CRF (see [Section 6.9](#)).
- 4) Subject will be reminded to notify the site in case of SAE (to Investigator: note that only fatal SAEs and related SAEs need to be reported at this visit).
- 5) The source documents and relevant CRF pages for this visit will be completed.

V07 (18 months +14 days after VAC2): Collection of Safety Information and Blood Sample - for Adult Subjects in Immunogenicity Persistence and Booster Phase Cohort 2

- 1) DC SAE will be checked by the Investigator/staff, different from the person performing vaccination.
- 2) A blood sample will be collected (6 mL).
- 3) Collect reportable categories 2 and 3 concomitant medications in the CRF (see [Section 6.9](#)).
- 4) Subject will be reminded to notify the site in case of SAE (to Investigator: note that only fatal SAEs and related SAEs need to be reported at this visit).
- 5) The source documents and relevant CRF pages for this visit will be completed.

V08 (between 24 and up to 36 months +14 days after VAC1): Collection of Safety Information, Blood Sample, and Booster Injection - for Adult Subjects in Immunogenicity Persistence and Booster Phase Cohort 2

- 1) DC SAE will be checked and collected by the Investigator/staff, different from the person performing vaccination.
- 2) Urine pregnancy test, if woman of childbearing potential.
- 3) Collect ongoing medications including other therapies in the source document and reportable concomitant medication in the CRF (see [Section 6.9](#)).
- 4) A blood sample will be collected (6 mL).
- 5) Conduct a physical examination, including temperature.
- 6) Obtain past and significant current medical history. Check contraindication for subsequent vaccinations (see [Section 5.2.7](#)).
- 7) Subjects will receive the booster injection (VAC3) from the unblinded staff member in the opposite arm as compared to VAC2 and will stay at the center for the 30-minute observation period following vaccination.
- 8) DC3 will be provided to the subject.
- 9) Subject will be reminded to notify the site in case of SAE and AESI.
- 10) For woman of childbearing potential: remind the subject to notify the site in case of pregnancy
- 11) The source documents and the relevant CRF pages for this visit will be completed.
- 12) Remind the subject to bring back the DC3 when they return for V09 at a specified date and time.

V09 ([between 24 months and up to 36 months+14D] +14 [+1] days after VAC1): Collection of Safety Information and Blood Sample - for Adult Subjects in Immunogenicity Persistence and Booster Phase Cohort 2

- 1) DC3 will be checked by the Investigator/staff.
- 2) A blood sample will be collected (6 mL).
- 3) Collect ongoing medications including other therapies in the source document and reportable concomitant medication in the CRF (see [Section 6.9](#)).
- 4) Subject will be reminded to notify the site in case of SAE and AESI.
- 5) The source documents and relevant CRF pages for this visit will be completed.

V10 ([between 24 months and up to 36 months+14D] +28 [±3] days after VAC1): Collection of Safety Information and Blood Sample - for Adult Subjects in Immunogenicity Persistence and Booster Phase Cohort 2

- 1) DC3 will be collected and checked by the Investigator/staff.
- 2) Conduct a physical examination.
- 3) Give the subject the MA to record any SAEs or AESIs that may occur during the safety follow-up.
- 4) Collect ongoing medications including other therapies in the source document and reportable concomitant medication in the CRF (see [Section 6.9](#)).
- 5) Subject will be reminded to notify the site in case of SAE or AESI.
- 6) The source documents and relevant CRF pages for this visit will be completed.
- 7) Complete the study termination record.

6-month Safety Follow-up PC after the Booster Injection (M30 up to M42 +14D): for Adult Subjects in Immunogenicity Persistence and Booster Phase Cohort 2

Subject will be contacted by phone by the Investigator/staff 6 months after the booster vaccination. Information recorded in MA will be checked.

Further details on the visit procedures can be found in the Operating Guidelines.

5.1.4.3 Follow-up for Cohorts 1 and 2

Follow-up of Subjects With RVNA Titer ≤ 0.5 IU/mL After Completion of the 2- or 3-dose PrEP Regimen With Rabies Vaccine (and Booster Dose for Adult Subset):

As stated in [Section 1.3.1](#), if a subject had RVNA titers < 0.5 IU/mL at all timepoints after the primary or booster series, the Investigator may decide based on clinical judgment to offer an additional single vaccination of a local licensed rabies vaccine (as chosen by the Investigator) and administer according to the local SmPC / Product Information (PI) or national guidelines, and if the subject / subject's LAR agree. Adult subjects randomized in the Immunogenicity Persistence

and Booster Phase Cohort 2 need to complete all the visits in this phase before being offered to receive benefit vaccine if the Investigator deemed necessary.

Follow-up of Subjects With Related AEs or With AEs That Led to Study/Vaccination Discontinuation:

Unless a subject or subject's parent/LAR refuses further contact, each subject who experiences an AE (whether serious or non-serious) during the study must be followed until the condition resolves, becomes stable, or becomes chronic (even after the end of the subject's participation in the study) if *either* of the following is true:

- The AE is considered by the Investigator to be related to the product administered
- The AE caused the discontinuation of the subject from the study or vaccination

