- 1) DC2 will be checked by the blinded Investigator/staff, different from the person performing vaccination.
- 2) Collect ongoing medications including other therapies in the source document and reportable concomitant medication in the CRF (see [Section 6.9](#)).
- 3) Conduct a physical examination, including temperature.
- 4) A blood sample will be collected (6 mL).
- 5) Remind the subject to notify the site in case of a SAE and AESI.
- 6) For woman of childbearing potential: remind the subject to notify the site in case of pregnancy.
- 7) Complete the relevant source document information and CRF pages for this visit.

V04 (35 [\pm 3] days after VAC1): Collection of Safety Information

- 1) DC2 will be collected and checked by the blinded Investigator/ staff, different from the person performing the vaccination.
- 2) Conduct a physical examination, including temperature.
- 3) Give the MA (to adult subjects who will only participate in Primary Series Cohort 2) or DC SAE (to adult subjects who will participate to the Immunogenicity Persistence and Booster Phase Cohort 2) to record SAEs or AESIs that may occur during the safety follow-up.
- 4) Collect ongoing medications including other therapies in the source document and reportable concomitant medication in the CRF (see [Section 6.9](#)).
- 5) Subject will be reminded to notify the site in case of SAE and AESI.
- 6) Complete the study termination record for adult subjects who will only take part to the Primary Series Cohort 2
- 7) The source documents and relevant CRF pages for this visit will be completed.

6-month Safety Follow-up PC (M6+14D) After the Primary Series – for Adult Subjects in Primary Series Cohort 2

- 1) Subject will be contacted by phone by the blinded personnel 6 months after the 2nd vaccination. Information recorded in MA1 will be checked.
- 2) Further details on the visit procedures can be found in the Operating Guidelines.

V05 (6 months +14D after VAC2): 6-month Safety Follow-up after the Primary Series and Blood Sample - for Adult Subjects in Immunogenicity Persistence and Booster Phase Cohort 2

- 1) DC SAE will be checked by the Investigator/staff, different from the person performing vaccination.
- 2) A blood sample will be collected (6 mL).
- 3) Collect reportable categories 2 and 3 concomitant medications in the CRF (see [Section 6.9](#)).
- 4) Subject will be reminded to notify the site in case of SAE and AESI.

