9.2.1.2 Safety Endpoints

The secondary endpoints for the evaluation of safety are:

- Occurrence of any unsolicited systemic AEs reported in the 30 minutes after each vaccine injection
- Occurrence of solicited (pre-listed in the subject's DC and electronic CRF) injection site and systemic reactions occurring within 7 days after each injection
- Occurrence of unsolicited (spontaneously reported) injection site reactions occurring within 28 days after each injection and unsolicited systemic AEs up to 28 days after each injection
- Occurrence of SAEs and AESIs within at least 6 months after each vaccination as applicable to Cohort 1 and Cohort 2.
- SAEs (including AESIs) reported throughout the study, including occurrence, nature (Medical Dictionary for Regulatory Activities [MedDRA] preferred term), time of onset, duration, intensity, action taken, relationship to the product administered (for systemic AEs only),

whether the event caused termination from the study, outcome, elapsed time from last administration (if less than 24h), relationship to study procedures, and seriousness criterion

Note: The following AESIs will be considered as SAEs and reported to the Sponsor: anaphylactic reactions, encephalitis, and convulsions. For each AESI, the standard case definitions from the Brighton Collaboration will be used. These AESIs have been defined based on existing post-marketing safety data of other rabies vaccines.

Note: Information about SAEs, AESIs, and cases of pregnancy were recorded throughout the study for pediatrics and adults in Cohort 1; and this is up to 6 months after the booster dose for subset of adults in Cohort 1. Information about SAEs, AESIs, and cases of pregnancy will be recorded until 6 months after the primary series (V05) and until 6 months after the booster dose for subset of adults in Cohort 2. Between the 6-month follow-up visit after primary series (V05) and booster dose visit (V08), AESIs will not be collected, only fatal SAEs and related SAEs will be collected.

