12.4 Interim / Preliminary Analysis

The statistical analysis will be performed in 4 steps:

- The 1st statistical analysis will be done once all immunogenicity data up to D28 (V03, 21 days after the 2nd vaccination) in the primary series of Cohort 2 and all safety data up to D35 (V04, 28 days after the 2nd vaccination) in the primary series of Cohort 2 are available (ie, at the end of 6-month safety follow-up after booster phase in Cohort 1; and up to D35 [V04] in primary series in Cohort 2). The randomization and vaccination exposure information for all enrolled subjects will be unblinded at the time of 1st statistical analysis.
- The 2nd statistical analysis will be carried out once the 12-month immunogenicity persistence data and safety data in Cohort 2 (V06) are collected.
- The 3rd statistical analysis will be carried out once all the immunogenicity and safety data up to 28 days after the booster vaccination in Cohort 2 (V10) are collected.
- The 4th statistical analysis will be carried out once the 6-month safety follow-up data post the booster vaccination in Cohort 2 (M30 up to M42) are collected.

No statistical adjustment is necessary because there are no repeat analyses of the same parameter.

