### ***Unsolicited Adverse Events***

The unsolicited systemic AEs will be analyzed per cohort:

- Cohort 1
  - “Between the first and the second vaccination”, which corresponds to AEs reported at V02 and occurring after the first dose \*
  - “Between the second and the third vaccination”, which corresponds to AEs reported at V03 and occurring after the second dose †
  - “Up to 28 days after the third vaccination”, which corresponds to AEs reported at V05 and occurring after the third vaccination
  - “Up to 28 days after any vaccine injection in the primary series”, which corresponds to AEs belonging to any of the above three categories
  - “Up to 28 days after booster dose”, which corresponds to AEs reported at V07 or V08 and occurring after booster dose, for an adult subset
- Cohort 2
  - “Between the first and the second vaccination”, which corresponds to AEs reported at V02 and occurring after the first dose \*
  - “Up to 28 days after the second vaccination”, which corresponds to AEs reported at V03 or V04 and occurring after the second vaccination
  - “Up to 28 days after any vaccine injection in the primary series”, which corresponds to AEs belonging to any of the above two categories
  - “Up to 28 days after booster dose”, which corresponds to AEs reported at V09 or V10 and occurring after booster dose, for an adult subset

The unsolicited injection site reactions will be analyzed within 28 days (from D0 to D28) after each vaccination, and within 28 days after any vaccination. An unsolicited injection site reaction

\* For subjects interrupting their vaccination schedule after the first injection, unsolicited AEs until 28 days after the first dose will be collected

† For subjects interrupting their vaccination schedule after the second injection, unsolicited AEs until 28 days after the second dose will be collected

(excluding SAE and AESI) reported with an onset > 28 days after a vaccination will not be included in the safety analysis, but will be listed separately.

The unsolicited systemic AEs will be analyzed between each vaccination if vaccinations are separated less than 28 days, or up to 28 days after each vaccination, if the next vaccination is interrupted, and up to 28 days after any vaccination. An unsolicited systemic AE (excluding SAE and AESI) reported with an onset > 28 days after vaccination will not be included in the safety analysis, but will be listed separately.

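### The visit that closes the 28-day unsolicited AE period may be held from day 25 and takes back the diary, so some subjects counted in the 28-day rates are not followed for 28 days

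*Protocol*

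**What the plan says.** **Endpoint.** Protocol Section 9.2.1.2 defines the endpoint as "unsolicited systemic AEs up to 28 days after each injection", with unsolicited "injection site reactions occurring within 28 days after each injection" alongside. Section 9.2.1.3.3 names the diary card as the instrument for the 28 days after the last primary dose and after the booster.

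**Closing visit.** In the Tables of Study Procedures, four visits end a 28-day period, each at last dose + 28 days with ±3 days: V05 and V08 in Cohort 1, V04 and V10 in Cohort 2. Section 5.1.4.2 words the last as "V10 ([between 24 months and up to 36 months+14D] +28 [±3] days after VAC1): Collection of Safety Information".

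**What happens there.** At V10, "DC3 will be collected and checked by the Investigator/staff", and the next instruction is "Give the subject the MA to record any SAEs or AESIs that may occur during the safety follow-up". The other three visits follow the same pattern. At Cohort 2 V04, for example, "DC2 will be collected and checked by the blinded Investigator/ staff, different from the person performing the vaccination", and the subject leaves with a memory aid or an SAE diary.

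**Later contact.** Protocol Section 11.1 describes the 6-month follow-up as a questionnaire on SAEs and AESIs.

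**Analysis.** SAP Section 5.1.2.2 labels the booster systemic-AE period as one "which corresponds to AEs reported at V09 or V10 and occurring after booster dose". It excludes non-serious events with onset after day 28, and its denominator for unsolicited events is everyone vaccinated at the dose. Protocol Section 12.4 treats V04 as day 28 when it requires that "all safety data up to D35 (V04, 28 days after the 2nd vaccination) in the primary series of Cohort 2 are available".

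**The concern.** The endpoint and the diary run to day 28, but a fully compliant visit can end diary recording up to three days sooner. From then on the subject holds a tool for SAEs and AESIs only. Where the next contact is the 6-month call, a non-serious AE starting on the uncovered days has no planned route into the database.

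The error runs one way. Visits on days 29 to 31 cannot offset early ones, because onsets after day 28 are left out of the analysis, while subjects seen early stay in the denominator at full weight. The SAP says its denominators are meant to avoid understating incidence, and on this point the schedule works against that aim.

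At stake are the absolute unsolicited AE rates. After a booster these are a stated safety objective, and every boosted subject receives VRVg-2, so no control booster is available against which to read them.

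**Working it through.** The plan gives no figure on this point to reproduce, so the check is a day count.

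**Inputs**
- Endpoint window: 28 days after each injection (Protocol 9.2.1.2).
- Closing visit: last dose + 28 days, ±3 days (Tables of Study Procedures; SAP Tables 3.2 to 3.5).
- Actual visit days and AE rates: not in the documents, so assumed below.

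**Largest loss for one subject**
- Earliest permitted day = 28 − 3 = 25.
- Days lost = 28 − 25 = 3, and 3/28 = 10.7%.
- This is the same for V05, V08, V04 and V10 when counted from the last dose.

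**Average loss, if visits are uniform over days 25 to 31 (assumption)**
- Days lost by visit day: 3, 2, 1, 0, 0, 0, 0.
- Share seen early = 3/7 = 43%.
- Mean loss = (3 + 2 + 1)/7 = 0.86 day, and 0.86/28 = 3.1%.

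**Effect on a reported rate, taking a true 28-day rate of 20% (illustration)**
- Onset uniform over the 28 days: 20% × (1 − 0.0306) = 19.4%.
- Constant hazard: the average over days 25 to 31 of 1 − 0.80^(min(day, 28)/28) is 19.45%.

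**Range, with uniform onset**

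| Visit pattern (assumed) | Reported rate |
|---|---|
| 10% of visits early, mean loss 2 days among them | 20% × (1 − 0.10 × 2/28) = 19.9% |
| 25% of visits early, mean loss 2 days among them | 20% × (1 − 0.25 × 2/28) = 19.6% |
| Uniform over days 25 to 31 | 19.4% |
| All visits on day 25 | 20% × 25/28 = 17.9% |

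**Who has no later visit**
- After V10 (Cohort 2 booster) and after Cohort 1 V08: everyone. Only the 6-month call remains.
- After Cohort 1 V05 and Cohort 2 V04: subjects outside the booster subsets.
- Booster-subset subjects return in person, at V06 in Cohort 1 and V05 in Cohort 2. Protocol Section 9.2.1.3 has staff ask at each visit about any AEs since the previous one, so their primary-series gap may be partly recovered.

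**With a window of +28 days, +3 days**
- Permitted days are 28 to 31, and the loss is 0 on every one.

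**The case against.** The strongest reply is that the effect is small and touches nothing confirmatory. A fall from 20% to 19.4% is 0.6 percentage point, whereas the exact 95% interval around 46/230 (20%) runs from 15.0% to 25.8%. Safety is descriptive, SAEs and AESIs continue to be collected, and the windows are the same in every vaccine group. All of this stands and sets the weight of the point. It does not remove the mismatch between the follow-up promised and the follow-up scheduled.

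Three stronger readings are tempting, and the documents do not support them.

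- **That the SAP discards AEs reported after the closing visit.** The phrase "which corresponds to AEs reported at V09 or V10 and occurring after booster dose" could be read so. But SAP Section 4.3.1 analyses unsolicited AEs up to 28 days after vaccination, Section 4.3.1.2.4 derives onset from the start date, and Section 5.1.2.2 excludes by onset day. No rule drops an event with onset by day 28 because it was reported late. The gap is in collection.
- **That no later contact asks about non-serious AEs.** The visit question in Protocol Section 9.2.1.3 contradicts this for the booster subsets after their primary series.
- **That the diary can close earlier than day 25.** The headings in Protocol Section 5.1.4 count from VAC1. Taken literally, V04 (day 35 − 3 = 32, dose 2 on day 8) could fall 24 days after dose 2, and V05 (day 56 − 3 = 53, dose 3 on day 31) 22 days after dose 3. The procedure tables count from the last dose, and Section 12.4 calls V04 28 days after the second vaccination. Day 25 is the supportable limit, and the two anchors need reconciling.

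The Operating Guidelines, to which Section 5.1.4 refers for further visit details, are not available and might contain a remedy. The protocol and SAP do not.

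**Conclusion.** The point holds as a minor, inexpensive improvement. For subjects whose only later contact is the 6-month SAE/AESI call, non-serious, non-AESI unsolicited AEs starting between an early closing visit and day 28 are not collected, and these subjects remain in the 28-day denominator. The day count (at most 3 of 28 days, 10.7%) follows from the documents. The average figures (43% early, 0.86 day, 3.1%, and 20% read as about 19.4%) rest on uniform visit days and an assumed AE rate. The true size depends on actual visit days, which are not given.

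The result is a slight understatement of absolute rates. A reader might go on to infer bias between vaccine groups, but the windows are identical across groups and nothing in the documents suggests that visit timing differs by group. No hypothesis test, power figure or per-protocol set is affected.

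**What to change.** 1. **V10.** Change the window from VAC3 + 28 days ±3 to VAC3 + 28 days +3 in the Table of Study Procedures, Protocol Section 5.1.4.2 and SAP Table 3.5. The cost is 4 permitted days instead of 7, so slightly more window deviations, and a V10 window that differs from the earlier closing visits. V10 has no blood draw in its steps or in the table. The Cohort 2 booster per-protocol set depends on V08 and V09 timing, so no immunogenicity data are put at risk.
2. **Completed phases.** For V05, V08 and Cohort 2 V04, tabulate by group how many closing visits fell before day 28, and repeat the any-unsolicited-AE rate in subjects followed to day 28. This costs one descriptive table.
3. **Wording.** Reconcile the VAC1-anchored headings in Protocol Section 5.1.4 with the last-dose anchors in the tables. Reconcile the mention of a blood sample in the V10 heading with the V10 steps, which list none. In SAP Section 5.1.2.2, align the visit-based period labels with the onset-date rule that the SAP already applies.

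A question about minor AEs at the 6-month call is not recommended, because recall over roughly five months would be unreliable.

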5.1.5 Planned Study Calendar

The following dates are approximate. The actual dates may differ as, for example, the study will not start until all the appropriate regulatory and ethical approvals have been obtained.

FVFS (first visit, first subject) to LCLS (last contact, last subject): October 2019 – September 2025

Inclusion period – FVFS to FVLS (first visit, last subject): October 2019 – February 2023

Primary vaccination period: October 2019 – February 2023

Booster vaccination period: October 2020 – March 2025

End of study Booster Phase Cohort 1: August 2021

End of study Immunogenicity Persistence and Booster Phase Cohort 2: September 2025

Date of Final Clinical Study Report: March 2026

5.1.6 End of study definition

A subject is considered to have completed the study if the subject has completed the last contact planned in the [Table of Study Procedures](#).

The end of the study is defined as the date that the last results have been released for samples collected at Visit 9, Cohort 2, related to primary and secondary endpoints. The end of the study must be achieved no later than 9 months after the last contact of the last subject in the study.

However, for periodic safety reports, the study is considered completed when the clinical study report is finalized.

